#### 10.2.2. Day 5 Visit

This visit will be performed for safety purposes. Patients will be instructed that they must take the Day 5 study drug dose at the clinic before 12:00 pm (noon), after the Holter monitor has been placed. The following assessments will be performed at the Day 5 visit for the first 75 randomized patients:

- Observation of patients predose and for the first 6 hours following dose administration, including hourly vital sign monitoring
- ECG predose and at Hour 6
- Continuous Holter monitoring 15 minutes predose and for 24 hours following dose administration

If clinically significant cardiac conduction abnormalities are not observed in the first 75 patients that are treated, Day 5 monitoring will be discontinued for the remaining patients enrolled in the study. After that time, the first-dose monitoring strategy should be repeated at Day 5 if any

cardiac safety issues were observed at Day 1. If any safety issues are identified during Day 5 monitoring, then the monitoring guidelines in Section 10.2.1.1 should be followed.

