#### Part B:

#### Safety (Secondary) Endpoints:

#### Part A

Cardiac safety and tolerability during initial dose titration will be evaluated in Part A patients according to the following monitoring schedule:

- Day 1 (all Part A patients): Observation of patients predose and for the first 6 hours following initial dose administration; ECG predose and at Hour 6; continuous Holter monitoring for 15 minutes predose and for 24 hours following dose administration.
- Day 5 (first 75 patients): Observation of patients predose and for the first 6 hours following dose administration; ECG predose and at Hour 6; continuous Holter monitoring for 15 minutes predose and for 24 hours following dose administration.
- Day 8 (first 75 patients): Continuous Holter monitoring for 15 minutes predose and for 24 hours following dose administration.

If clinically significant heart rate reductions or cardiac conduction abnormalities are not observed in the first 75 patients that are treated, Day 5 and Day 8 monitoring will be discontinued for the remaining patients enrolled in the study.

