Target AEs of interest in study RPCS 001 were closely monitored and included bradycardia and other heart conduction abnormalities, pulmonary toxicity, hepatotoxicity, macular edema, and suicidal ideation. No AEs were reported for LFT elevation, macular edema, or suicidal ideation. Two subjects who received 2 mg RPC1063 for 7 days had Grade 1 pulmonary-related adverse events of obstructive airways disorder. For the two subjects, forced vital capacity (FVC) and forced expiratory volume at 1 second (FEV1) declined to >20% below their baseline values on Day 7 (last dosing day) and Day 14 (last post-dose follow-up visit). Subjects were followed and values returned to baseline off therapy.

Four subjects had Grade 2 cardiac-related AEs of bradycardia and/or conduction abnormality. One subject experienced a Grade 2 second degree AV block and associated nausea after receiving a single dose of 1.5 mg RPC1063 that led to study discontinuation. At a dose of 3 mg RPC1063, 2 subjects reported AEs of Grade 2 sinus arrest, and 1 subject reported an AE of sinus bradycardia. These events resolved within 24 hours with no medical intervention.

All subjects, including those administered placebo, showed an initial reduction in HR following dosing on Day 1. Subjects who received RPC1063 had a greater decrease in HR compared to placebo subjects, and there was evidence of a dose-dependent decrease in absolute heart rate. Lower doses of RPC1063 led to less change in absolute heart rate over time, with the greatest change from baseline during the first 12 hours following treatment of 5.2 bmp and -13.2 bpm for doses of 0.3 mg and 1 mg, respectively. In general, most of the decrease in HR was observed within the first 6 hours after study drug was administered.

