There are a number of AEs associated with fingolimod treatment that may limit its use in the RMS population. Cardiac AEs such as bradycardia and other heart conduction abnormalities have been observed with fingolimod in the clinical development program and in the postmarketing setting, which increased the need for more intensive cardiac monitoring for RMS patients when receiving the first dose of fingolimod. Elevations in liver enzymes (3 times the upper limit of normal [ULN]) have also been observed in the range of 8-12%, consistent with liver pathology (Cohen, 2010; Kappos, 2006). These toxicities may be a consequence of the drug lacking specificity for S1P1R, from having higher than necessary exposures, or from having pharmaceutic liabilities related to fingolimod's structural class. Additionally, due to complex absorption, distribution, metabolism and excretion properties including an extremely long half-life (89 to 157 hours), the PD effects of fingolimod are prolonged, with patients requiring several weeks before the number of circulating lymphocytes return to normal following cessation of treatment (Kovarik, 2004; Budde, 2002). This may have clinical safety consequences, particularly if patients develop infections or other treatment-related complications.

All of the currently approved drugs have therapeutic, safety and/or logistical limitations. All but fingolimod are administered by injection, presenting challenges associated with injection-related AEs, compliance and convenience. First-line therapies have modest efficacy coupled with side effect profiles that affect patient quality of life and adherence to therapy. Second- and third-line therapies have better efficacy profiles but significant safety issues. There is a pressing need for an MS treatment that is highly effective, well tolerated, and orally active.

A clinical development program for RPC1063 is being pursued in MS because: (i) it is a potent and selective orally bioavailable S1P1R agonist, (ii) it has a short half-life allowing for rapid clearance of the drug in the setting of potential treatment related complications, (iii) it may allow for a more rapid recovery of lymphocytes into the normal range in RMS patients, and (iv) RPC1063 may have an improved safety and tolerability profile over existing RMS therapies including other S1PR agonists.

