#### **Exploratory Endpoints:**

## 8.2.2. Safety (Secondary) Endpoints

#### Part A

Cardiac safety and tolerability during initial dose titration will be evaluated in Part A patients according to the following monitoring schedule:

- Day 1 (all Part A patients): Observation of patients predose and for the first 6 hours following initial dose administration; ECG predose and at Hour 6; continuous Holter monitoring for 15 minutes predose and for 24 hours following dose administration.
- Day 5 (first 75 patients): Observation of patients predose and for the first 6 hours following dose administration; ECG predose and at Hour 6; continuous Holter monitoring for 15 minutes predose and for 24 hours following dose administration.

• Day 8 (first 75 patients): Continuous Holter monitoring for 15 minutes predose and for 24 hours following dose administration.

If clinically significant heart rate reduction or cardiac conduction abnormalities are not observed in the first 75 patients that are treated, Day 5 and Day 8 monitoring will be discontinued for the remaining patients enrolled in the study.

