#### 10.2.3. Day 8 Visit

This visit will be performed for safety purposes. Patients will be instructed that they must take the Day 8 study drug dose at the clinic before 12:00 pm (noon), after the Holter monitor has been placed. Continuous Holter monitoring will be performed for 15 minutes predose and for 24 hours following dose administration for the first 75 randomized patients.

If clinically significant cardiac conduction abnormalities are not observed in the first 75 patients that are treated, Day 8 monitoring will be discontinued for the remaining patients enrolled in the study. The first-dose monitoring strategy should be repeated at Day 8 if any cardiac safety issues were observed at Day 5. See the monitoring guidelines in Section 10.2.1.1 for further details.

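### Sections 10.2.2 and 10.2.3 leave heart rate reduction out of the condition for ending routine Day 5 and Day 8 cardiac monitoring in Part A, while the Synopsis, Section 8.2.2 and Table 1 include it

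*Protocol*

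**What the plan says.** Five places in the protocol state when routine Day 5 and Day 8 cardiac monitoring ends in Part A.

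- **Both findings named.** The Synopsis (Safety Endpoints, Part A) and Table 1 footnote 1 use the condition "If clinically significant heart rate reductions or cardiac conduction abnormalities are not observed in the first 75 patients that are treated". Section 8.2.2 has "If clinically significant heart rate reduction or cardiac conduction abnormalities are not observed in the first 75 patients that are treated".
- **Conduction only.** Section 10.2.2 has "If clinically significant cardiac conduction abnormalities are not observed in the first 75 patients that are treated, Day 5 monitoring will be discontinued". Section 10.2.3 has "If clinically significant cardiac conduction abnormalities are not observed in the first 75 patients that are treated, Day 8 monitoring will be discontinued".

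The count of 75 and the consequence for the remaining patients are the same in all five. No section says which wording governs.

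**The concern.** A heart rate fall is the effect the protocol expects from this drug class (Section 12.4), and hourly vital signs are part of the Day 5 visit (Section 10.2.2). Yet the two sections that describe the Day 5 and Day 8 visits omit heart rate from the group-level decision.

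The condition pools the first 75 patients over roughly 100 to 125 planned sites (Section 9.1), so it has to be applied centrally, and whoever applies it has two texts. If the visit sections are followed to the letter, the result is the less protective action: routine monitoring at the two dose steps (to 0.5 mg on Day 5, and to 1 mg on Day 8 in the high-dose arm) could end despite a clinically significant bradycardia in the first 75 patients.

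**Working it through.** The plan gives no figure to reproduce. The check is a comparison of texts, followed by simple counts.

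**1. The two conditions by case.** Consider what could be seen in the first 75 treated patients, taking both wordings literally.

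| Seen in the first 75 | Synopsis, 8.2.2, Table 1 fn 1 | 10.2.2, 10.2.3 |
|---|---|---|
| Neither finding | Met: stop | Met: stop |
| Conduction abnormality only | Not met | Not met |
| Both findings | Not met | Not met |
| Heart rate reduction only | Not met | Met: stop |

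The wordings part company in the last row only. What follows when the condition is not met is not written anywhere; that monitoring would continue is an inference.

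**2. Can the last row occur?** Section 7.2.4 reports "Four subjects had Grade 2 cardiac-related AEs of bradycardia and/or conduction abnormality". These were 1 second degree AV block, 2 sinus arrests and 1 sinus bradycardia: 1 + 2 + 1 = 4. The last is described as "and 1 subject reported an AE of sinus bradycardia". So the findings can separate. That case was at 3 mg, and 3 mg / 1 mg = 3 times the top Part A dose, so it gives no rate for Part A.

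**3. Is the short wording only shorthand?** Two places point that way. Section 7.2.4 describes the target events as "closely monitored and included bradycardia and other heart conduction abnormalities", and Section 7.3 says "Cardiac AEs such as bradycardia and other heart conduction abnormalities have been observed with fingolimod"; both treat bradycardia as a kind of conduction abnormality. Against this, the Phase 1 sentence quoted in step 2 separates the two. Section 10.2.1.1 lists a heart rate below 45 bpm and new second degree or higher AV block as separate triggers for extended monitoring. Naming heart rate in three of the five statements of this rule would be redundant if the conduction term already covered it.

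**4. Reach if the decision is open.** Planned Part A enrolment is 210. Patients after the first 75: 210 - 75 = 135, and 135 / 210 = 64%. This is a ceiling.

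**5. Is the decision likely to be open?** Inputs are planned dates and counts from the Synopsis and from the Part B schedule in Table 3 and Section 9.3.

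- At the Part A interim, 80% to 90% of 210 are treated: 0.80 × 210 = 168 and 0.90 × 210 = 189. Both exceed 75, so the decision comes before the interim.
- Part B starts only after the interim is reviewed.
- Part B needs 104 weeks of treatment plus 4 weeks of follow-up, 108 weeks in all. Counting back from a planned end in May 2017, the last Part B patient would be randomized by about early May 2015.
- Version 4.0 is dated 01 October 2014, about seven months before that.

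Unless all of the roughly 1200 Part B patients were to be randomized within those seven months, Part B was already under way at Version 4.0 and the 75-patient decision was past. These are planned dates, not confirmed status.

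**The case against.** The strongest reply is that the difference is editorial and probably has no live effect. The fuller condition appears three times, including in the footnote to the schedule of assessments. Whoever applies the rule centrally has the Synopsis and Section 8.2.2 to hand, and an independent data monitoring committee reviews safety. None of the five statements defines what is clinically significant, so judgement drives the decision under either wording. On the planned dates the decision was taken before this version. All of this stands, and it limits the consequence.

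The visit text does not ignore heart rate for the individual patient. Any safety issue on Day 5 sends the site to Section 10.2.1.1, whose triggers include low heart rate. A cardiac issue on Day 1 brings repeat monitoring on Day 5, and one on Day 5 brings it on Day 8. Every Part A patient has 24-hour Holter monitoring on Day 1, and Phase 1 titration showed little further heart rate fall after Day 4. A reader might infer that bradycardia would go unmonitored; the documents do not support that. What these safeguards leave open is narrower. Once routine Day 5 monitoring stops, a patient with an uneventful Day 1 has no scheduled Day 5 cardiac observation that could trigger monitoring on Day 8.

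Two other stronger readings also fail. A reader might count the 210 - 189 = 21 to 210 - 168 = 42 patients still untreated at the interim as exposed to an open choice. By then the decision has already been applied from patient 76 onward. A reader might also take Table 5 footnote 1 and the ECG and Holter text in Section 11.2.1 as a third, unconditional rule. They are scheduling statements that leave the condition out, and they need no change.

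**Conclusion.** The inconsistency is real and should be corrected. Three statements of the rule require the absence of both findings and two require the absence of one. They lead to different actions if a clinically significant heart rate reduction occurs without a conduction abnormality. The shorthand reading is possible but weak.

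The consequence is modest. If the decision is open, up to 135 of 210 patients could be affected, assuming full planned enrolment. If it has been made, as the planned dates suggest, this is a matter of documentation. The documents give no basis for a probability that the two wordings would have produced opposite decisions. No endpoint, error rate or power calculation is involved. Part B and its SAP are unaffected.

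**What to change.** In Sections 10.2.2 and 10.2.3, add heart rate reductions to the condition so that it matches the Synopsis and Table 1 footnote 1. If the 75-patient decision has already been made, record which rule was applied and what had been observed; that costs one note.

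The edit is one phrase in two sections, but Section 16.2 treats any protocol change as an amendment, with submission to regulators and ethics committees. The operational cost arises only if a qualifying heart rate reduction occurs without a conduction abnormality while the decision is open. Taking the condition as not met to mean that monitoring continues, up to 135 further patients would have Day 5 and Day 8 monitoring. That is up to 135 × 2 = 270 further 24-hour Holter recordings, plus the six-hour Day 5 observation for each patient.

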#### 10.2.3. Day 8 Visit

This visit will be performed for safety purposes. Patients will be instructed that they must take the Day 8 study drug dose at the clinic before 12:00 pm (noon), after the Holter monitor has been placed. Continuous Holter monitoring will be performed for 15 minutes predose and for 24 hours following dose administration for the first 75 randomized patients.

If clinically significant cardiac conduction abnormalities are not observed in the first 75 patients that are treated, Day 8 monitoring will be discontinued for the remaining patients enrolled in the study. The first-dose monitoring strategy should be repeated at Day 8 if any cardiac safety issues were observed at Day 5. See the monitoring guidelines in Section 10.2.1.1 for further details.

#### 10.2.4. Day 29 (Week $4 \pm 3$ days) Visit

The following assessments will be performed at the Week 4 visit:

- Blood/urine sampling for the following laboratory tests:
  - Hematology: RBC count, total and differential WBC count (basophils, eosinophils, lymphocytes, monocytes, and neutrophils), platelet count, hemoglobin, hematocrit, MCV, MCH, and MCHC.
     Note: All total WBC and differential WBC counts will be blinded during the study.
  - Blood chemistry: sodium, potassium, chloride, calcium, magnesium, phosphate, blood urea nitrogen, random glucose, albumin, alkaline phosphatase, creatinine, SGPT/ALT, SGOT/AST, GGT, amylase, total bilirubin, conjugated bilirubin. Abnormal laboratory parameters inconsistent with clinical presentation of MS or suspicious of underlying medical condition should be repeated for accuracy. If an increase of amylase above the clinically notable value (≥ 300 U/L) is observed at any post randomization visit, lipase should be tested to determine the origin of elevated amylase (pancreatic versus extra pancreatic).
  - Urine beta-hCG (females of childbearing potential only). If the urine pregnancy test is positive, do not dose and confirm with a serum pregnancy test.
  - Standard PK sampling: PK samples are to be taken 2 to 6 hours following administration
- Vital signs: body temperature, blood pressure and heart rate
- 12-lead ECG
- Dispense study drug and patient diary
- Review study drug accountability and compliance
- Suicidality assessment using the C-SSRS
- Record concomitant therapy

Record AEs/SAEs

#### 10.2.5. Day 57 (Week $8 \pm 3$ days) Visit

The following assessments will be performed at the Week 8 visit:

- Urine beta-hCG (females of childbearing potential only). If the urine pregnancy test is positive, do not dose and confirm with a serum pregnancy test.
- Vital signs: body temperature, blood pressure and heart rate
- Dispense study drug and patient diary
- Review study drug accountability and compliance
- Brain MRI
- Suicidality assessment using the C-SSRS
- Record concomitant therapy
- Record AEs/SAEs

#### 10.2.6. Day 85 (Week $12 \pm 3$ days) Visit

Note: Subjects are to be instructed not to take their dose of study drug at home, and will be administered study drug at the clinic after laboratory procedures have been completed. Subjects should arrive at the clinic in a fasted state.

The following assessments will be performed at the Week 12 visit:

- Blood/urine sampling for the following laboratory tests:
  - Hematology: RBC count, total and differential WBC count (basophils, eosinophils, lymphocytes, monocytes, and neutrophils), platelet count, hemoglobin, hematocrit, MCV, MCH, and MCHC
     Note: All total WBC and differential WBC counts will be blinded during the study.
  - Blood chemistry: sodium, potassium, chloride, calcium, magnesium, phosphate, blood urea nitrogen, random glucose, albumin, alkaline phosphatase, creatinine, SGPT/ALT, SGOT/AST, GGT, amylase, total bilirubin, conjugated bilirubin. Abnormal laboratory parameters inconsistent with clinical presentation of MS or suspicious of underlying medical condition should be repeated for accuracy. If an increase of amylase above the clinically notable value (≥ 300 U/L) is observed at any post randomization visit, lipase should be tested to determine the origin of elevated amylase (pancreatic versus extra pancreatic)
  - Urine beta-hCG (females of childbearing potential only). If the urine pregnancy test is positive, do not dose and confirm with a serum pregnancy test.
  - Standard PK sampling: PK sample is to be taken prior to dose administration
- Administer study drug
- Vital signs: body temperature, blood pressure and heart rate

- 12-lead ECG
- Dispense study drug and patient diary
- Review study drug accountability and compliance
- Brain MRI
- EDSS and neurological examination
- MSFC AND LCLA
- Pulmonary function tests including FEV1 and FVC measurements
- Suicidality assessment using the C-SSRS
- Record concomitant therapy
- Record AEs/SAEs

#### 10.2.7. Day 113 (Week $16 \pm 3$ days) Visit and Day 141 (Week 20) Visit

The same assessments will be performed at the Week 16 visit and the Week 20 visit, as follows:

- Urine beta-hCG (females of childbearing potential only). If the urine pregnancy test is positive, do not dose and confirm with a serum pregnancy test.
- Vital signs: body temperature, blood pressure and heart rate
- Dispense study drug and patient diary
- Review study drug accountability and compliance
- Brain MRI
- Suicidality assessment using the C-SSRS
- Record concomitant therapy
- Record AEs/SAEs

# 10.2.8. Day 169 (Week 24 ± 3 days) Visit

The Week 24 visit will be the end of study visit for patients who do not choose to continue participating in the optional blinded extension period. After all Week 24 visit procedures have been completed, patients who choose to continue will be re-consented and re-randomized in a blinded fashion to receive the RPC1063 dose titration regimen (if on placebo) or continue on their RPC1063 treatment assignment. First dose monitoring procedures will be followed in all patients as described in Section 10.2.1. Patients participating in the optional blinded extension period will be instructed that they must take the first study drug dose at the clinic before 12:00 pm (noon). The first dose and cardiac monitoring procedures for the blinded extension treatment will be performed on a separate day up to 7 days following the Week 24 visit.

The following assessments will be performed at the Day 169 (Week 24) visit:

• Blood/urine sampling for the following laboratory tests:

- Hematology: RBC count, total and differential WBC count (basophils, eosinophils, lymphocytes, monocytes, and neutrophils), platelet count, hemoglobin, hematocrit, MCV, MCH, and MCHC
   Note: All total WBC and differential WBC counts will be blinded during the study.
- Blood chemistry: sodium, potassium, chloride, calcium, magnesium, phosphate, blood urea nitrogen, random glucose, albumin, alkaline phosphatase, creatinine, SGPT/ALT, SGOT/AST, GGT, amylase, total bilirubin, conjugated bilirubin,. Abnormal laboratory parameters inconsistent with clinical presentation of MS or suspicious of underlying medical condition should be repeated for accuracy. If an increase of amylase above the clinically notable value (≥ 300 U/L) is observed at any post randomization visit, lipase should be tested to determine the origin of elevated amylase (pancreatic versus extra pancreatic)
- Urinalysis: leukocytes, specific gravity, bilirubin, blood, glucose, ketones, pH, protein, and urobilinogen
- Urine beta-hCG (females of childbearing potential only). If the urine pregnancy test is positive, do not dose and confirm with a serum pregnancy test.
- Coagulation panel: PT and PTT
- sTSH
- Standard PK sampling: PK samples are to be taken 2 to 6 hours following administration
- Complete physical examination: including evaluation of heart, lung, head and neck, abdominal, neurological, skin, and extremities
- Weight
- Vital signs: body temperature, blood pressure and heart rate. For patients who choose to continue on the blinded extension period, the first dose monitoring procedures must be performed, including recording of baseline (predose) heart rate and blood pressure (see Section 10.2.1)
- 12-lead ECG. For patients who choose to continue on the blinded extension period, the Day 1 first dose monitoring procedures must be performed (see Section 10.2.1).
- Review study drug accountability and compliance
- Randomize in case patient chooses to continue on the blinded extension period
- If the patient chooses to continue in the study to the blinded extension period, dispense study drug (including titration kit) and patient diary, and administer dose of study drug at the site

- Brain MRI
- and neurological examination.

•

- MSQOL-54
- Pulmonary function tests including FEV1 and FVC measurements, and DLCO
- OCT evaluation
- Dermatological examination
- Suicidality assessment using the C-SSRS
- Record concomitant therapy
- Record AEs/SAEs

Patients who terminate study at this visit will be scheduled for a follow-up visit 4 weeks  $(\pm 5 \text{ days})$  after last dose.

Patients who choose to continue on the blinded extension period will be scheduled for a safety visit 14 days after first dose of the blinded extension period.

